#### CDR (Clinical Dementia Rating)

The CDR will be administered to the participant and informant, at screening, week 24 and week 48 and will be administered by a certified tester. During the CDR is a structured interview protocol that assesses a patient's cognitive and functional performance in six areas: memory, orientation, judgment & problem solving, community affairs, home & hobbies, and personal care. Scores in each of these are combined to obtain a composite score ranging from 0 through 3. The CDR can discern very mild impairments, based on informant interview and short task-based participant responses.

#### Canadian Occupational Performance Measure (COPM)

COPM is a client-centered, standardized, criterion-referenced outcome measure which allows for individualized treatment implementation. The COPM is administered via a semi-structured interview with caregivers at baseline, Week 4, and 8 week follow up. The COPM is a multidisciplinary health assessment that assesses all areas of the participants' occupational performance, including self-care, leisure, and instrumental activities of daily living. Caregivers identify areas of concern or that need improvement, and the top five activities are rated for performance and satisfaction. Caregiver rating of performance and satisfaction of self-identified activities will be used in statistical analysis.

## Situational Assessment of Activity and Function (SAAF)

The SAAF is a new assessment created by current study PI ([name]) to gain better insights on the situational characteristics that cause behavioral reactions in persons with dementia. The SAAF was developed from initial data collection of the current study. The SAAF is 120 questions to be completed by caregivers of persons with cognitive impairment and will take approximately 15 minutes to complete. Questions are review caregiver perceptions of the activity performance of the person they care for in various activities (i.e., cooking, dressing, community mobility, etc.) The assessment is completed electronically using Redcap survey emailed to caregivers. Use of the SAAF is in this study is to glean initial reactions from caregiver participants regarding their ease of use and to determine time length of administration. The use of the SAAF in this study will be completed using REDCap public survey link. This feature allows individuals to complete the survey, but does not associate a record ID to answers, all responses are anonymous. Data from survey item responses will not be stored, saved, reviewed or analyzed. Caregivers currently enrolled in this study will be asked to voluntarily complete the electronic survey if they would like. It is not required. Participants will be asked to disclose the length of time it took to complete the form and to document any initial perceptions of the ease of use of the form and/or its perceived applicability.

## Attachments

Attach Type	File Name
DataCollection	CDR.pdf
DataCollection	Behavior journal.pdf
DataCollection	COPM.pdf
DataCollection	Form M Sensory.pdf
DataCollection	MoCA-Test-English_7_1.pdf
DataCollection	ZBI-22_AU1.0_eng-USori_ReviewCopy-1.pdf
DataCollection	Vineland-3 Interview (002).pdf
DataCollection	hpiq-questionnaire.pdf
DataCollection	SituationalAssessmentOfActivit.pdf

**Resources:** Describe what resources/facilities are available to perform the research (i.e., staff, space, equipment). Such resources may include a) staffing and personnel, in terms of availability, number, expertise, and experience; b) psychological, social, or medical services, including counseling or social support services that may be required because of research participation; c) psychological, social, or medical monitoring, ancillary care, equipment needed to protect subjects; d) resources for subject communication, such as language translation services, and e) computer or other technological resources, mobile or otherwise, required or created during the conduct of the research. Please note: Some mobile apps may be considered mobile medical devices under FDA regulations (see [FDA Guidance](#)). Proximity or availability of other resources should also be taken into consideration, for example, the proximity of an emergency facility for care of subject injury, or availability of psychological support after participation.

Research activities conducted at performance sites that are not owned or operated by the University of Kentucky, at sites that are geographically separate from UK, or at sites that do not fall under the UK IRB's authority, are subject to special procedures for coordination of research review. Additional information is required (see [IRB Application Instructions - Off-Site Research](#) web page); supportive documentation can be attached in the E-IRB "Additional Information" section. Provide a written description of the role of the non-UK site(s) or non-UK personnel who will be participating in your research. The other site may need to complete its own IRB review, or a cooperative review arrangement may need to be established. Contact the Office of Research Integrity at [contact] if you have questions about the participation of non-UK sites/personnel.

If the University of Kentucky is the lead site in a multi-site study, or the UK investigator is the lead investigator, describe the plan for managing the reporting of unanticipated problems, noncompliance and submission of protocol modifications and interim results from the non-UK sites.

Resources for this study include research assistants and medical staff at SBCoA. University of Kentucky Telemedicine office will provide technical support needed for secure access to Zoom conferencing. Data will be uploaded and saved to REDCap the day of researcher acquisition following completion. REDCap is a password-protected, secure data management web application in the secure data center run by the Institute for Pharmaceutical Outcomes and Policy (IPOP) physically located in the new Biological and Pharmaceutical Complex building at the University of Kentucky. REDCap will be accessed using password-protected computers issued by the University of Kentucky. Intervention materials will be purchased by SBCoA administrative staff and mailed via UPS shipping to participants' homes.

[name] from Eastern Kentucky University, Department of Occupational Science and Occupational Therapy will be included in this study. Her role will be to serve as an occupational therapy consultant if needed during development of individualized sensory protocols, during treatment for consultation for sensory procedures if questions from participants arise and PI is not able to independently address questions, and during data analysis. [name] will have access to recorded patient videos. An IRB Authorization Agreement with EKU will be sought.

**Potential Risks:** Describe any potential risks or likely adverse effects of the drugs, biologics, devices or procedures subjects may encounter while in the study. Please describe any physical, psychological, social, legal or other risks and assess their likelihood and seriousness.

There is minimal risk involved in participation of this study. Potential for minimal risk is associated with possibly sensory system overload associated with interventions. Signs of sensory overload include neurophysiological changes (sweating, dizziness, changes in balance, pallor, pupil dilation, yawning), emotional and behavioral changes (fearful responses, avoidance, irritability, anxiety, angry outbursts, aggression, agitation), and cognitive changes (increased confusion, decreased orientation to time, place, self, etc.), and decreased attention span (more than typical). Monitoring of sensory overload will be monitored by caregivers following training of

intervention techniques, psychosocial stress and burden to the individual with dementia and their caregiver during and the presence of the researcher during observation. Interventions may include topical lotions which may cause skin irritation, rash, or dermatitis. Caregivers will be trained to observe patient for any signs of discomfort, sensory overload, or skin irritation, distress or anxiety. If a participant/caregiver shows signs of distress or anxiety, the researcher will provide the participant/caregiver with a break. If the participant wishes to proceed then another topic may be discussed, if not the interview or observation will be rescheduled for a different date.

[Back to Top](#)

**Safety Precautions:** Describe the procedures for protecting against or minimizing any potential risks, *including risks of breach of confidentiality or invasion of privacy*. Where appropriate, discuss provisions for ensuring necessary medical or professional intervention in the event of adverse events, or unanticipated problems involving subjects. Also, where appropriate, describe the provisions for monitoring the data collected to ensure the safety of subjects. If vulnerable populations other than adults with impaired consent capacity are to be recruited, describe additional safeguards for protecting the subjects' rights and welfare.

The procedures for protecting against and minimizing any potential risks of breach of confidentiality or invasion of privacy during the research will require each individual with dementia, their LAR, and the caregiver to review and sign the consent and confidentiality agreements. All study conduct will occur using procedures outlined and validated by the University of Kentucky Telemedicine office. Contact information for [name] (SBCOA Clinical director) and SBCOA social workers will be kept on file and accessible during data collection in the field in case issues or concerns arise during intervention visits. Collected data will be de-identified and all data will be kept in a password-protected computer for a period of six years, then destroyed via deletion of files.

**Benefit vs. Risk:** Describe potential benefits to the subject(s); include potential benefits to society and/or general knowledge to be gained. Describe why the risks to subjects are reasonable in relation to the anticipated benefit(s) to subjects and in relation to the importance of the knowledge that may reasonably be expected to result. If you are using vulnerable subjects (e.g., impaired consent capacity, pregnant women, etc...), justify their inclusion by describing the potential benefits of the research in comparison to the subjects' vulnerability and the risks to them. For information about inclusion of certain vulnerable populations, see the IRB/ORI Standard Operating Procedure for Protection of Vulnerable Subjects [C3.0100] [\[PDF\]](#).

There are no direct benefits to subjects. Risks to participants, both caregivers and those with dementia, are minimal, including possible discomfort with sensory-based intervention implementation.

**Available Alternative Treatment(s):** Describe alternative treatments and procedures that might be advantageous to the subjects, should they choose not to participate in the study. This should include a discussion of the current standard of care treatment(s).

Not applicable.

[Back to Top](#)

**Research Materials, Records and Privacy:** Identify the sources of research material obtained from living human subjects. Indicate what information (specimens, records, data, genetic information, etc.) will be recorded and whether use will be made of existing specimens, records or data. Explain why this information is needed to conduct the study.

*Return of Research Results or Incidental Findings (if applicable):*

If research has the potential to identify individual results or discover incidental findings that could affect the health of a subject, describe plans to assess, manage, and if applicable disclose findings with individual subjects or provide justification for not disclosing. For IRB expectations, refer to the UK IRB "Frequently Asked Questions (FAQs) on the Return of Research Results or Incidental Research Findings" [\[PDF\]](#).

All materials, except behavior journals, will be in electronic format. Materials will include consent agreements (hard copy mailed to participants), Adult Sensory Profile Questionnaire, Zarit Caregiver Burden Scale, COPM results, VABS results, CDR, NPI, Actigraph, MOCA, video recordings, and electronic case report files including medication, medical and neurological examination results, and adverse events. These forms will be uploaded and saved to REDCap the day of acquisition from participants. Hard copies of behavior journals will be electronically scanned and will be destroyed via shredding following uploading to REDCap. REDCap is a password-protected, secure data management web application in the secure data center run by the Institute for Pharmaceutical Outcomes and Policy (IPOP) physically located in the new Biological and Pharmaceutical Complex building at the University of Kentucky. The files will be stored for a period of six years per UK Policy A13-050. Digital audio recordings and electronic transcription of all interviews will be obtained. These electronic files will also be stored on REDCap. Upon enrollment in the study, subjects will be given pseudonyms to protect confidentiality and de-identify data.

**Confidentiality:** Specify where the data and/or specimens will be stored and how the researcher will ensure the privacy and confidentiality of both. Please address the following items or indicate if the following has been addressed in a HIPAA or Limited Review form:

- physical security measures (e.g., locked facility, limited access);
- data security (e.g., password-protection, data encryption);
- who will have access to the data/specimens and identifiers;
- safeguards to protect identifiable research information (e.g., coding, links, certificate of confidentiality);

- procedures employed when sharing material or data, (e.g., honest broker if applicable, written agreement with identify, measures to ensure that subject identifiers are not shared with recipients).
- management after the study

Describe whether data/specimens will be maintained indefinitely or destroyed. If maintained, specify whether identifiers will be removed from the maintained information/material. If identifiers will not be removed, provide justification for retaining them. If the data/specimens will be destroyed, describe how and when the data/specimens will be destroyed. For multi-site studies, the PI consults the study sponsor regarding retention requirements, but must maintain records for a minimum of six years after study closure. Also, specify who will access the identified data/specimens, and why they need access. If applicable, describe what measures will be taken to ensure that subject identifiers are not given to the investigator. If applicable, describe procedures for sharing data/specimens with entities not affiliated with UK (If the research is non-sponsored you need a data use agreement to share data/specimens [[Transfer Agreements](#)]).

**HIPAA/FERPA Minimal Access Standards:** The IRB expects researchers to access the minimal amount of identifiers to conduct the study and comply with applicable HIPAA and Family Educational Rights and Privacy Act (FERPA) requirements. If data are going to be collected, transmitted, and/or stored electronically, for appropriate procedures please refer to the guidance document "Confidentiality and Data Security Guidelines for Electronic Data" [[PDF](#)].

**Cloud storage:** For storage of data on cloud services other than UK OneDrive, please verify security settings are sufficient and in accordance with respective departmental, UK Corporate Compliance, and/or UK Information Technology requirements.

**Creation of digital data application/program:** If a research protocol involves the creation and/or use of a computer program or application, mobile or otherwise, please specify whether the program/application is being developed by a commercial software developer or the research team and provide any relevant information regarding the security and encryption standards used, how data is stored and/or transmitted to the research team, what information about the subjects the program/application will collect, etc. For relevant information to include, see Considerations for Protocol Design Concerning Digital Data [[PDF](#)]. The IRB may require software programs created or used for research purposes be examined by a consultant with appropriate Internet technology expertise to ensure subject privacy and data are appropriately protected.

**NIH-funded genomic research:** The National Institutes of Health (NIH) [Genomic Data Sharing \(GDS\) Policy](#) sets forth expectations that ensure the broad and responsible sharing of genomic research data consistent with the informed consent of study participants from which the data was obtained. If you are submitting genomic data to an NIH data repository, describe your NIH data sharing plan.

**Management after study:** Describe how the collected data/specimens will be managed after the end of the study. Specify whether identifiers will be removed from the maintained information/material. If identifiers will not be removed, provide justification for retaining them and specify what steps will be taken to secure the data/specimens (e.g., maintaining a coded list of identifiers separate from the data/specimens).

If the data/specimens will be destroyed, describe how, when, and why this will be done. Note that destruction of primary data may violate [NIH](#) and [NSF](#) retention and sharing requirements, journal publication guidance, and [University Data-Retention policies](#). Additionally, primary data may be necessary for other purposes (to validate reproducibility, for data sharing, or for evidence in various investigations). PIs should carefully consider whether the destruction of data is justified.

The investigator is responsible for retaining signed consent and assent documents and IRB research records for at least six years after study closure, as outlined in the Study Closure SOP [[PDF](#)]. If the research falls under the authority of the FDA or other regulatory agencies, or a study sponsor is involved, additional requirements may apply.

[Back to Top](#)

Each participant will be assigned a participant number and pseudonym, which will be used to identify the person during data analysis and when managing data. This de-identified human subject data will be stored on REDCap. Records maintained by SBCoA are not UK medical records, and so PHI and PII will not be used. At the conclusion of the study, all individual data will be stripped of identifying information and stored on REDCap, a secure location, for a period of 6 years, after which deletion of electronic files will destroy it. The IRB determined all video recording/electronic data must be destroyed using the University of Kentucky's Policy for Reuse and Disposal of Electronic Media. UK Healthcare Policy and Procedure A13-050 states "all electronic media shall be erased (i.e. purged) using data overwriting software that conforms to the requirements stated in NIST SP800-88." Confidentiality will be maintained, however, in the case in which abuse or concern of participants' safety, the researcher is required by law to report to authorities.

[Back to Top](#)

**Payment:** Describe the incentives (e.g., inducements) being offered to subjects for their time during participation in the research study. If monetary compensation is offered, indicate how much the subjects will be paid and describe the terms and schedule of payment. (It is IRB policy that provision should be made for providing partial payment to subjects who withdraw before the completion of the research. Monetary payments should be prorated or paid in full.)

No monetary incentive will be provided for participation in this study. Intervention kits will be mailed to participants for all arms of the study. These materials will not be returned to the researcher following study completion and kept by caregiver or patient, decided at their discretion.

**Costs to Subjects:** Describe any costs for care associated with research (including a breakdown of standard of care procedures versus research procedures), costs of test drugs or devices, and research procedure costs that are the subject's responsibility as a consequence of participating in the research. Describe any offer for reimbursement of costs by the sponsor for research related injury care.

This study requires participant use of personal device with webcam and Zoom video conferencing capability. Costs may be associated with cellular use or internet use while operating Zoom platform for this study.

**Data and Safety Monitoring:** The IRB requires review and approval of data and safety monitoring plans for greater than minimal risk research, or NIH-funded/FDA-regulated clinical investigations.

If you are conducting greater than minimal risk research, or your clinical investigation is NIH-funded/FDA-regulated, describe your Data and Safety Monitoring Plan (DSMP). [Click here for additional guidance on developing a Data and Safety Monitoring Plan.](#)

If this is a *non-sponsored investigator-initiated* protocol considered greater than minimal risk research, or your clinical investigation is FDA-regulated, *and* if you are planning on using a Data and Safety Monitoring Board (DSMB) as part of your DSMP, [click here for additional guidance](#) for information to include with your IRB application.

If relying on an independent agent or committee for DSMB services, it is the PI's responsibility to establish the services with the agent or committee. Please be reminded that the PI must submit DSMB reports to the IRB via modification or continuing review. i

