**Individualized Environmental Design Protocol:** Participants' caregivers will receive standard recommendations of physical environment modifications and caregiving techniques. Physical environmental modifications will include declutter living space, reduce background noise, increase natural light, accommodate for accessibility to commode and areas for drinking and eating. Caregiving techniques will include training for calming demeanor (emotional contagion), needs-driven care to decrease onset of behavioral disruption, and accepting and accommodating approach to behavioral disruption. Individualized sensory stimulation kits will be developed using subjects' preferred sensory stimuli (as determined by the Adult Sensory Profile assessment) and behavioral concerns identified in the COPM. One target behavior and/or time period of the day will be targeted for improvement. Selection of items included in the individualized sensory kit will be determined based on the attached decision tree and sensory mode plans. The sensory kit will be provided via caregiver administration or supervision two scheduled times (once in the morning and once in the afternoon) per day and one time as needed prior to activity or task associated with behavior concern to promote maintained behavioral regulation and adaptive responses.

**Data Analysis:** Due to the nature of feasibility of this study, sample size of 30 participants with cognitive impairment (10 per arm) does not fully power the study. Statistical description of behavior change results will be explorative and descriptive in nature. Per-protocol analysis (PPA) will be performed with 75% or more adherence to program as determined from weekly visits and journals. Power analyses for secondary outcome measures cannot be performed as this study is a preliminary investigation of these secondary outcome measures.

Summary statistics will be tabulated for the behavior change, protocol adherence, and adverse events. The frequencies of behavior change, protocol adherence, and adverse events will be compared between participants within same group and between group for differences.

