#### Neuropsychiatric Inventory

The NPI-Q will be administered with the caregiver at baseline, week 4, and week 8. The NPI-Q is a commonly used behavior assessment tool for persons with cognitive impairment.[63] This tool was selected in order to best represent behaviors characteristic of cognitive impairment. The assessment includes 12 behavioral and psychiatric domains including delusions, hallucinations, irritability, anxiety, agitation, depressions, dysphoria, apathy, disinhibition, aberrant motor behavior, appetite/eating changes, and night-time behaviors. The care provider rates these behaviors based on severity of the impact on the patient on a scale of 1 (mild), 2 (moderate), or 3 (severe). The care provider also rates distress to themselves caused by each behavior on a scale from 0 (not distressing at all) to 5 (extreme or very distressing). Both behavior severity and caregiver distress will be used in analysis.

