#### DATA AND SAFETY MONITORING PLAN

The Principle Investigator (PI, [name]) and Faculty Advisor ([name], PhD) will be responsible for monitoring the data and safety of participants along with their co-investigators.

a. Periodic Review: The PI and faculty advisor will hold bi-weekly meetings for the first two months of enrollment, then monthly for four more months, and quarterly thereafter. The faculty advisor will review all minor AE and SAE reported to date of review. The staff meetings will include the PI, co-investigators, and lay co-workers in charge of assessment. The meetings will include evaluation of all research procedures, fidelity to protocol, discussion of newly enrolled participants, and review of status of all formally enrolled participants including all adverse events. Adverse events will be reviewed to determine if changes in the protocol are indicated. Participant demographics to date, recruitment progress, difficulties encountered during enrollment, an update on data entry, and any other issues or concerns that have arisen since the last research team meeting will also be discussed.

In addition to review of all research procedures and AE/SAE, specific review of risk related to behavioral condition of the patient and related to the intervention will be completed at meetings. Review will assess:

1. Risk to behavioral condition: Weekly checks via Zoom video conferencing of behavioral tracking will occur with PI and participants. If substantial behavioral change is noted by caregiver or patient report, this behavior change will be reviewed with faculty advisor.

2. Risk of Intervention: Weekly checks via Zoom video conferencing with participants will assess adverse events and patient complaint related to the intervention tools. We anticipate the following potential areas of concern:

- a. Lotions-minor dermatological reaction
- b. Exercise cards-muscle soreness, fall during exercise
- c. Snacks-possible choking hazard
- d. Actigraph wear-skin irritation at wear site (wrist)
- e. Scents of lotion-headache
- f. Gel lap pad-strain from lifting 3 pound lap pad.

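### Adverse events are compared between arms, but training to spot overload signs is tied to the intervention and not described for controls, so detection may differ and one behaviour can count as both harm and outcome

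*Combined protocol and SAP*

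**What the plan says.** **The comparison.** The Data Analysis paragraph of the Research Description states: "The frequencies of behavior change, protocol adherence, and adverse events will be compared between participants within same group and between group for differences". It names no test for adverse events and gives no rule for when a behaviour is an adverse event. The sample is 30, 10 per arm, and is acknowledged not to be fully powered. The separate Statistical Analysis section does not mention adverse events.

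**The harm to be watched for.** Potential Risks names the source: "Potential for minimal risk is associated with possibly sensory system overload associated with interventions". Its behavioural signs include "emotional and behavioral changes (fearful responses, avoidance, irritability, anxiety, angry outbursts, aggression, agitation", alongside physical and cognitive signs. On who watches, the section says "Monitoring of sensory overload will be monitored by caregivers following training of", and the sentence runs on to intervention techniques. It then adds: "Caregivers will be trained to observe patient for any signs of discomfort, sensory overload, or skin irritation, distress or anxiety".

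**The outcome.** The Neuropsychiatric Inventory section says: "The assessment includes 12 behavioral and psychiatric domains including delusions, hallucinations, irritability, anxiety, agitation". The caregiver is the informant at baseline, week 4 and week 8, and both severity and caregiver distress are analysed.

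**The arms.** The Control Group paragraph gives usual care and a short home-safety pamphlet, offers a sensory kit only after follow-up, and describes no caregiver training. The paragraphs on the two active arms both include caregiver training directed at behavioural disruption.

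**Safety collection.** Study Design and Research Procedures provide for weekly adverse-event review without naming an arm. In the Data and Safety Monitoring Plan, the item on intervention risk says that the weekly checks "will assess adverse events and patient complaint related to the intervention tools".

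**The concern.** A between-arm comparison of adverse events can be read only if the same event has the same chance of being noticed and reported in every arm. Here the caregiver is a main source of reports. The plan links teaching of the warning signs to training in the intervention, and the safety item on intervention risk asks about tools that controls, by the Control Group paragraph, do not have during the study.

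The signs are also not specific to the intervention. Participants are enrolled because a caregiver reports behavioural difficulty (inclusion criterion 9), so irritability, anxiety and agitation are expected background. The same episode could be logged as an adverse event, tallied as a behaviour change and scored on the NPI-Q, with nothing saying which count it belongs to.

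At stake is the tolerability message of a feasibility trial. If active-arm caregivers report more of the same background behaviour, the intervention looks less well tolerated than it is. The counts also have uses beyond a table: the section on modification or termination makes frequent events beyond mild severity in more than 30% of participants a trigger for reviewing the intervention, and links some withdrawals to events attributed to it. Background behaviour can be attributed to a sensory kit only where there is one.

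**Working it through.** The plan gives no adverse-event rate, detection rate, alpha or power, so there is no figure on this point to reproduce. Its one relevant number, the sample size, agrees with itself: 3 arms × 10 = 30.

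**Step 1: overlap of harm and outcome.** Setting the overload signs in Potential Risks beside the NPI-Q domains, three terms appear word for word in both: irritability, anxiety and agitation. The Data and Safety Monitoring Plan sends substantial behavioural change to the faculty advisor but does not say when such a change becomes an adverse event. Double recording is therefore possible. No text says that it will happen.

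**Step 2: ascertainment by arm.**
- Pointing to a difference: overload is described as a risk of the interventions; monitoring follows training in intervention techniques; the Control Group paragraph describes no training; most of the listed anticipated concerns are kit items (lotions, exercise cards, snacks, lap pad).
- Pointing to no difference: the sentence on caregiver training names no arm; Visit 3 training in Research Procedures names no arm; weekly adverse-event review names no arm; the monitoring plan records every observed or reported event regardless of presumed cause.
- Unresolved: Research Procedures mails intervention materials to all participants and the Payment section mails kits in all arms, while the Control Group paragraph defers the kit until after follow-up.

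**Step 3: what unequal detection would do (illustration; every input is assumed).** Let p be the true proportion with at least one such event, equal in all arms, and d1 and d0 the detection probabilities in an active arm and in control.
- Recorded proportion = p × d.
- Apparent risk ratio = (p × d1)/(p × d0) = d1/d0.
- Apparent risk difference = p × (d1 − d0).

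With d1 = 0.9 and p = 0.4, and the chance of a false difference taken by exact enumeration of a two-sided Fisher test at an assumed 0.05:

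| d0 | Recorded per 10, active | Recorded per 10, control | Risk ratio | Risk difference | False difference, 10 v 10 | False difference, 20 v 10 |
|---|---|---|---|---|---|---|
| 0.9 | 3.6 | 3.6 | 1.00 | 0 | 1.3% | 3.2% |
| 0.7 | 3.6 | 2.8 | 1.29 | 0.08 | 1.8% | 4.3% |
| 0.5 | 3.6 | 2.0 | 1.80 | 0.16 | 4.0% | 8.7% |
| 0.3 | 3.6 | 1.2 | 3.00 | 0.24 | 8.9% | 17.6% |

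The last column pools the two active arms. Over p from 0.2 to 0.8 and the three unequal values of d0, the apparent risk difference runs from 0.2 × (0.9 − 0.7) = 0.04 to 0.8 × (0.9 − 0.3) = 0.48.

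**The case against.** The strongest reply is that safety collection is arm-neutral. Study Design, Research Procedures (Visits 4 to 8) and the monitoring plan have staff asking every caregiver about adverse events each week; behaviour journals are kept daily with no arm limit; and the monitoring plan's behavioural-risk item applies to all participants. In the item on intervention risk, the reference to tools may qualify only the complaints and not the adverse events. Regular staff-led questioning reduces dependence on what the caregiver was taught. This stands, and it is why a difference in detection is possible and not shown. It does not close the point: an event has to be noticed and judged worth mentioning before it is recorded, and the plan does not say that the same signs are asked about in the same way in each arm.

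A reader might infer that only active-arm caregivers are taught the signs, and that a control episode would appear on the NPI-Q alone. The documents do not support that. The training sentence names no arm, the sentence linking monitoring to intervention training is garbled, and the rule to record all events covers controls. The attached detailed protocol, which is not among these documents, may say more about training content.

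A reader might also infer that overload signs will be coded as adverse events. Potential Risks describes risks; it is not an adverse-event definition. Nor is it wrong in itself for a worsening symptom to appear in both a safety log and an outcome scale. What is missing is a statement of how the two are kept apart when the arms are compared.

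Finally, the practical reach is limited: 10 per arm, no named test, and no adverse-event analysis in the Statistical Analysis section. That is fair, but a descriptive table carries the same bias as a test.

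**Conclusion.** The point holds in a limited form. The plan intends a between-arm comparison of adverse events, ties training in the warning signs to the intervention, describes none for controls, and has no rule separating an adverse event from an NPI-Q outcome for three shared behaviours. Detection may therefore differ by arm, and one behaviour can be recorded as both harm and outcome.

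The size of any bias is unknown. It is zero if detection is equal, and the risk ratios and differences above rest wholly on assumed detection and event rates. The more natural reading has active-arm caregivers prompted more, which would count against the active arms. The direction is not certain, since the same training also encourages an accepting approach to disruption. The overlap with the NPI-Q does not depend on how the training text is read. With a descriptive comparison of 10 per arm, this is an inexpensive improvement to the safety comparison, not a flaw that undermines the trial.

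**What to change.** - At the existing weekly calls, use one arm-neutral checklist of the signs in Potential Risks, and give caregivers in all three arms the same instruction on what to report.
- Base the between-arm comparison of adverse events on the checklist events.
- Ask about tool-related complaints separately and report them descriptively for the active arms.
- State in Data Analysis that irritability, anxiety and agitation may appear both as checklist events and as NPI-Q scores, and that the two are reported as separate measures.
- Reconcile the Control Group paragraph, Research Procedures and the Payment section on what controls receive and when.
- Leave the monitoring plan's recording of all adverse events unchanged.

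A rule counting a sign only if it exceeds baseline NPI-Q severity should not be used. A domain already rated 3, the maximum, could not register worsening; signs such as sweating or pallor have no NPI-Q domain; and it could narrow the recording of all events.

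The cost is a one-page checklist, some protocol wording, a few more minutes per control visit and more events recorded in controls. The checklist equalises prompting; it does not remove the influence of caregivers knowing what they deliver. Where data are already collected, the report should say how events were elicited in each arm and caution against reading a between-arm difference as harm.
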